## 6.3.3 Variables

The following variables will be collected for each AE;

- AE (verbatim)
- The date when the AE started and stopped
- Maximum intensity of the AE
- Whether the AE is serious or not
- Investigator causality rating against the Investigational Product (yes or no)
- Action taken with regard to investigational product
- Outcome.

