#### **3.4.1** Adverse events

Adverse events experienced by the subjects will be collected throughout the entire study and will be coded by the AstraZeneca designee using the latest version of the Medical Dictionary for Regulatory Activities (MedDRA).

Adverse event data will be categorized according to their onset date into the following study periods:

- AEs occurring during run-in (onset date  $\geq$  Visit 1 and before the first dose of IP)
- AEs occurring during treatment (onset date  $\geq$  the first day of IP and  $\leq$  the last day of IP + 2 weeks)
- AEs occurring post-treatment (onset date > the last day of IP + 2 weeks and  $\leq$  Visit 11 (Week 26))

The timing of AEs will be assigned to the period in which they first occurred. If an AE has a missing onset date, then unless the stop date of the AE indicates otherwise, this will be considered an on treatment event. Similarly, if an AE has a partial onset date, then unless the partial onset date or the stop date indicates otherwise, this will be considered an on treatment AE. The same 'during treatment' definition will be used for laboratory and physical examination data, where applicable.

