## 4.2.9.1 Adverse events (AEs)

AEs will be summarized separately for the treatment and study periods. AEs occurring during the run-in period, or occurring post-treatment (as per the definition in Section 3.4.1) will be listed, but not summarized separately.

An overall summary table will be produced showing the number and percentage of subjects with at least 1 AE in any of the following categories; AEs, SAEs, deaths due to AE, AEs causing discontinuation of IP (DAEs), and other significant AEs (OAEs). OAEs will be defined following medical review of system organ classes/preferred terms after unblinding of the data. The total number of AEs in the different AE categories in terms of AE counts will also be presented (ie, accounting for multiple occurrences of the same event in a subject).

AEs will be summarized by SOC and PT assigned to the event using MedDRAversion 20.0. For each PT, the number and percentage of subjects reporting at least one occurrence will be presented ie, for a subject multiple occurrences of an AE will only be counted once.

AEs (by SOC and PT) will be summarized by causality and maximum intensity. If a subject reports multiple occurrences of the same AE, the maximum intensity will be taken as the

highest recorded maximum intensity (the order being mild, moderate, and severe). AEs with missing intensity will not be outputted in this table.

The following will also be summarized by SOC and PT

SAEs OAEs in the category of safety topics of special attention DAEs DAEs causally related to IP SAEs leading to discontinuation of IP Most common AE's (frequency of >3%) (by PT only) Deaths Severe Infections Severe infections will be identified as AEs that have been entered into the infection modules in the eCRF (INFDI, INFRF and INFSS).

Injection site reactions will be reported by preferred term for the treatment period, summarized by treatment group.

The approach to identifying anaphylaxis/hypersensitivity AEs occurring within 3 days of IP administration is described in a separate charter. Those identified AEs meeting the criteria described in this charter will be summarized by preferred term and treatment group for the treatment period and study period.

Subjects experiencing a severe infection are defined as having an AE which met one of the following:

- life-threatening,
- requiring hospitalisation,
- requiring treatment with antiviral medications, intravenous antibiotics or medications for helminth parasitic infections,

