- permanent discontinuation of study drug.

Severe infections will be summarized by MedDRA high level group term, high level term and preferred term by treatment group for the treatment period and study period.

The rate of AEs per person-years at risk, calculated as (number of subjects reporting AE)/(total time at risk of AE), will also be reported. Rates will typically be expressed in terms of events per 100 subject-years. Total time at risk will be defined as the date of last visit in the 12-week treatment period – date of randomization +1.

Separate listings of subjects with AEs, SAEs, death due to AE, discontinuations due to AEs, or severe infections will be presented.

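### SAP 4.2.9.1 leaves ungraded AEs out of the causality and maximum-intensity table, so a treatment-related AE with no grade can be missing from every planned causality summary

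*SAP*

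**What the plan says.** SAP 4.2.9.1 sets out the AE tables. The one at issue is introduced as follows: "AEs (by SOC and PT) will be summarized by causality and maximum intensity". For repeat occurrences of the same AE in a subject, the grade shown is the "highest recorded maximum intensity (the order being mild, moderate, and severe"). The next sentence is the exclusion: "AEs with missing intensity will not be outputted in this table". The section gives no missing category, no footnote count and no worst-case assignment.

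The general SOC/PT table has no such restriction: "For each PT, the number and percentage of subjects reporting at least one occurrence will be presented". The only other summary that uses causality is the one headed "DAEs causally related to IP", which is limited to AEs that led to discontinuation of study drug. Listings are also planned: "Separate listings of subjects with AEs, SAEs, death due to AE, discontinuations due to AEs, or severe infections will be presented".

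Protocol 6.3.3 collects "Maximum intensity of the AE" for each AE and, as a separate item, the investigator's yes/no rating of causality against the investigational product.

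**The concern.** The exclusion drops a known value because a different field is blank. An AE can have a valid causality rating and no intensity grade. As written, the SAP then leaves out the whole AE, including its causality rating, from the only causality summary that covers all AEs.

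Two consequences follow. First, subject counts in this table can fall below those in the SOC/PT table, with no note to explain the gap. Second, an ungraded occurrence can never raise the maximum that is displayed. Both effects run in one direction only. At stake is the completeness of one descriptive safety table in a trial with small arms, where a single subject is visible in a percentage.

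**Working it through.** The documents state no figure for missing AE intensity, so there is none to reproduce. The check applies the rule literally and then sizes one lost subject.

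**Inputs**
- Ungraded AEs are not output in this table; repeats take the highest recorded grade (SAP 4.2.9.1).
- The SOC/PT table counts subjects with at least one occurrence and has no intensity restriction (SAP 4.2.9.1).
- Causality and intensity are separate variables (Protocol 6.3.3).
- 40 subjects are to be randomized per arm (SAP 1.3).

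**Step 1: an invented example.** These five subjects are for illustration only. The SAP does not say how causality is assigned when occurrences differ; here a subject counts as related if any occurrence was rated related.

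| Subject | AEs |
|---|---|
| A | Headache, related, ungraded |
| B | Headache, mild, unrelated; Headache, related, ungraded |
| C | Headache, unrelated, ungraded; Cough, moderate, unrelated |
| D | Headache, severe, related |
| E | Headache, moderate, related; Headache, related, ungraded |

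**Step 2: count with and without ungraded AEs.**

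| Count of subjects | All AEs | Ungraded AEs left out |
|---|---|---|
| Headache | 5 (A, B, C, D, E) | 3 (B, D, E) |
| Any AE | 5 | 4 (B, C, D, E) |
| Any related AE | 4 (A, B, D, E) | 2 (D, E) |

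- A leaves the whole table, because A has no graded AE at all.
- C leaves the Headache row but stays in the table through Cough.
- B stays in the Headache row as mild and unrelated; the related occurrence is gone.
- B and E are shown at their highest recorded grades, mild and moderate. The true maximum is at least that, and is not known to be higher.

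**Step 3: where a related, ungraded AE can still be seen.** If it led to discontinuation, it is in the summary of related DAEs. If it did not, it is in the overall AE summary, the SOC/PT table and the listings, but in no causality summary.

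**Step 4: the size of one lost subject.** With k affected subjects in an arm of 40, the loss is k/40. This gives 1/40 = 2.5%, 2/40 = 5.0% and 3/40 = 7.5%. These values of k are illustrative and have no source in the documents. The actual denominator is the safety set, which may differ slightly from 40.

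**Step 5: how the plan treats other missing values.** The SAP 4.2.9.2 shift tables show a missing category for each laboratory parameter, so the layout asked for here is already in use elsewhere in the plan.

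**The case against.** The strongest reply is that the rule may never act. Intensity is collected for every AE, and Protocol 9.4 provides for missing data to be queried and resolved, for source data verification, and for investigator sign-off before lock. If no grade is missing, nothing is excluded and the tables reconcile. This stands, and it is why the point is minor.

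The exclusion is also confined to one descriptive table on which no test or decision depends. A reader might infer that ungraded AEs vanish from safety reporting, or that the incidence of a term reported once is lost. The documents do not support that: the overall and SOC/PT tables and the listings carry no such exclusion. A reader might also infer that a subject with one ungraded AE disappears from this table. That happens only if every AE the subject had is ungraded; otherwise only rows with no graded occurrence are affected. Nor can it be said that a repeat event is shown at too low a grade, since the highest recorded grade may be the true maximum.

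The wording could also mean two summaries, one by causality and one by intensity, in which case the exclusion might not reach the causality counts. The singular reference to a table favours one cross-table but does not settle it.

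Two further arguments should not be pressed. Nothing in the documents indicates imbalance between arms. And the rule in SAP 3.4.1, beginning "If an AE has a missing onset date, then unless the stop date of the AE indicates otherwise", which counts such an event as on treatment, is no contradiction: an undated event must be placed in some period to be counted by period, which is a different problem from an unknown grade.

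What remains after all this is the loss of a recorded causality rating for an unrelated reason.

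**Conclusion.** The point holds conditionally and is a free improvement. The conditions are that some ungraded AEs remain at database lock and that a single table is meant. Under them, the table can only under-count, may not reconcile with the SOC/PT table, and leaves a related, ungraded, non-discontinuing AE out of every planned causality summary. Each affected subject is 2.5 percentage points of a 40-subject arm. The number affected cannot be estimated from the documents and is probably very low, possibly none. No efficacy result and no overall AE incidence is affected.

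**What to change.** In SAP 4.2.9.1, replace the exclusion sentence with:

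> AEs with missing intensity are kept in the table and counted under causality as recorded. A subject with no graded occurrence of a PT is shown under a Missing intensity category. Where at least one occurrence is graded, the highest recorded grade is shown, and the number of subjects per arm who also have an ungraded occurrence is footnoted.

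A subject with a recorded mild or moderate grade should not be moved to Missing because a repeat is ungraded, since that would hide a known grade. In the invented example, the new rule puts all 5 subjects in the Headache row: A and C under Missing, B mild, E moderate and D severe. The 4 subjects with a related AE are all counted, and the footnote reports 2 (B and E).

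The cost is one SAP sentence, one table column and one footnote. If no grades are missing, the column is empty.

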#### 4.2.9.2 Laboratory data

All continuous laboratory parameters will be summarized by absolute value at each visit by treatment group, together with the corresponding changes from baseline. The summary statistics presented will be the minimum, 1st quartile, median, 3rd quartile, maximum, mean and SD. Mean changes from baseline over time will also be plotted by treatment group.

Central laboratory reference ranges will be used for the identification of individual clinically important abnormalities, and a shift table will be produced for each laboratory parameter to display low, normal, high, and missing values. The shift tables will present baseline and maximum/minimum on-treatment value, as applicable for each parameter.

Shift plots showing each individual subject's laboratory value at baseline and at maximum/minimum will be produced for each continuous laboratory variable. If any laboratory variables show any unusual features (high or low values or a general shift in the data points) at other time points then shift plots of these data may be produced. A diagonal line indicating no change, and horizontal and vertical reference lines indicating the limits of the reference ranges will also be displayed on the shift plots.

Data for subjects who have treatment-emergent changes outside the predefined criteria will be presented. This data presentation will include all visits for this subset of subjects. A change is treatment-emergent if it occurred during treatment, using the same definition as in Section 3.4.1.

The frequency of changes with respect to normal ranges between baseline and each posttreatment time point will be tabulated. Frequencies of clinically noteworthy values (using reference ranges) occurring during the clinical study will also be given.

In order to identify potential Hy's Law cases, maximum post baseline TBL will be plotted against maximum post baseline ALT, expressed as multiples of ULN. This plot will be repeated to show maximum post baseline TBL against maximum post baseline AST, expressed as multiples of ULN. These plots will be produced on a log scale and reference lines will be included at 2xULN for TBL and at 3xULN for ALT/AST.

For all subjects who meet the biochemical criteria for Hy's law (potential Hy's Law), a Subject Safety Narrative will be produced, and the relevant laboratory parameters will be tabulated showing all visits for these subjects. Subjects with elevated ALT or AST, and elevated TBL, at any time may be explored further graphically using individual subject profile plots.

For urinalysis data, a shift table will be generated to present changes from baseline to last observation in the on-treatment period (as defined in Section 3.4.1). The number of subjects with treatment-emergent changes will also be summarized. Here, treatment-emergent changes are defined as None/Trace at baseline to Positive at any visit after baseline.

Any data outside the central laboratory reference ranges will be explicitly noted on the listings that are produced.

# 4.2.9.3 ECGs

The Investigator's assessment of the 12-lead ECG (normal or abnormal) will be listed for all subjects, along with detailing whether any abnormalities were clinically significant or not.

The number and percentage of subjects with clinically significant abnormal ECGs will be summarized by treatment group and visit.

# 4.2.9.4 Physical Examination

Shift tables (normal, abnormal (same as Visit 1, new or aggravated) of Visit 1 versus last observation during treatment will be generated, presenting the assessment for each component of the complete physical examination separately.

A similar shift table (normal, abnormal) of baseline (typically Visit 3) versus the last observation during treatment will also be generated.

Listings of results will be produced, including the date of assessments of the brief physical exam.

# 4.2.9.5 Vital Signs

All vital signs parameters will be summarized by absolute value at each visit by treatment group, together with the corresponding changes from baseline. The summary statistics presented will be the minimum, 1st quartile, median, 3rd quartile, maximum, mean and SD.

AstraZeneca defined reference ranges will be used for the identification of individual abnormalities, and a shift table will be produced for each vital signs parameter to display low, normal, high, and missing values. The shift tables will present baseline and maximum/minimum during treatment value, as applicable for each parameter.

Shift plots showing each individual subject's vital signs value at baseline and at maximum/minimum will be produced for each continuous vital signs parameter.

A shift table will be generated to present changes from baseline to last observation during study.

Data for subjects who have treatment-emergent changes outside the predefined criteria will be presented, using AstraZeneca clinically important change criteria. This data presentation will include all visits for each parameter with treatment-emergent changes for this subset of subjects. A change is treatment-emergent if it occurred during treatment, using the same definition as in Section 3.4.1.

All recorded vital signs data will be listed.

### 4.2.9.6 Pregnancy test

Number and percentage of subjects with positive urine pregnancy test will be summarised by visit.

### 4.2.9.7 Analysis of Immunogenicity variables

All analyses on Immunogenicity variables will be based on the safety analysis set. The overall ADA status for each subject will also be classified and summarized by treatment group. A subject will be categorised as overall ADA positive, if they have a positive ADA status at any point during the study (including baseline), otherwise a subject will be overall ADA negative. The association of overall ADA status across the study with AEs/SAEs will be evaluated . The following ADA results may be evaluated as proportion of subjects in cohorts together with corresponding titer summaries.

- Subjects who are ADA positive at any time (including baseline).
- Subjects who are ADA positive at baseline only.
- Subjects who are ADA positive at baseline and positive in at least one post baseline measurement.
- Subjects who are positive at baseline regardless of post-baseline result.
- Subjects who are ADA positive post-baseline.
- Subjects who are ADA positive post-baseline and ADA negative at baseline.
- Subjects who are persistently positive; persistently positive is defined as at least 2 post-baseline ADA positive measurements (≥ 16 weeks apart) or an ADA positive result at the last available assessment..
- Proportion of subjects who are transiently positive; transiently positive is defined as at least one post-baseline ADA positive measurement and not fulfilling the conditions for persistently positive.

For ADA, all subjects with titer information will be shown in the data listing, by dose level.

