---------------------------------------------------------------------------------------------------------------------------------------------------------------------	-----------------------------------------------------------------------------------------------------------------------------------------------------------------------------------------------------------------------------------------------------------------------------------------------------------------------------------------------------------------------------
To evaluate the effect of tralokinumab on symptom metrics of rhinosinusitis in adult subjects with asthma inadequately controlled with ICS	Change from baseline up to week 12 in Sino- Nasal Outcome Test -20 (SNOT-20) total score
To evaluate the pharmacokinetics and immunogenicity of tralokinumab	Pharmacokinetic parameters: Trough concentration (C _{trough} )
	Immunogenicity outcome variables: incidence rate of positive anti-drug antibodies and characterization of their neutralizing potential
To evaluate the effect of tralokinumab on Ribonucleic Acid (RNA) in samples obtained from adult subjects with asthma inadequately controlled with ICS.	

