## 6.7 Management of IP related toxicities

Appropriate drugs, such as epinephrine, H1 and H2 antihistamines, and corticosteroids, as well as medical equipment to treat acute anaphylactic reactions must be immediately available when IP is being administered. Study site personnel must be trained to recognize and treat anaphylaxis (Lieberman P et al 2010). Details on anaphylaxis management are provided in Appendix F.

Anaphylaxis will be defined as serious reaction that is rapid in onset and may cause death (Sampson HA et al 2006). Anaphylaxis typically manifest as 1 of 3 clinical scenarios:

- The acute onset of a reaction (minutes to hours) with involvement of the skin, mucosal tissue or both and at least one of the following: a) respiratory compromise; or
  b) reduced blood pressure or symptoms of end-organ dysfunction
- 2. Two or more of the following that occur rapidly after exposure: involvement of the skin/mucosal tissue, respiratory compromise, reduced blood pressure or associated symptoms and/or persistent gastrointestinal symptoms
- 3. Reduced blood pressure after exposure.

In order to help understand the potential drug-relatedness of any acute reaction, a blood sample should be drawn during the event for anti-drug antibody/neutralizing anti-body (ADA/nAb) testing. If an anaphylactic reaction occurs, a blood sample will be drawn from the subject as soon as possible after the event, at 60 minutes  $\pm$  30 minutes after the event, and at discharge for analysis of serum tryptase. The sample will be tested at the local lab or central laboratory where applicable.

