# **3.5** Calculations or derivation of Pharmacokinetic and Immunogenicity variables

Blood samples (processed to serum) for PK and immunogenicity assessments will be collected from all subjects at baseline prior to first IP administration at Week 0 (Visit 3) and at Week 12 (Visit 9) before IP administrations (except for visit 9, where there is no drug administration). ADA assessments will be conducted utilizing a tiered approach (screen, confirm, titer). These validated methods are conducted using a bridging assay format and statistically determined floating screening assay cut point factor and confirmatory assay cut point. The minimal sample dilution is 1:13. Titer values are reported as the reciprocal of the highest dilution that yields a value above the cut point. Samples from pre-defined study time points that confirm positive for ADA will also be tested for neutralizing ADA (nAb) activity. Both ADA and nAb will be summarized using descriptive statistics as described in Section 4.2.9.67.

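### The overall ADA status that SAP 4.2.9.7 ties to AEs/SAEs does not isolate treatment-emergent antibodies: pre-dose positives count as positive, and some subjects never tested after dosing count as negative

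*SAP*

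**What the plan says.** SAP 4.2.9.7 classes a subject as overall ADA positive if positive "at any point during the study (including baseline), otherwise a subject will be overall ADA negative". The next commitment is firm: "The association of overall ADA status across the study with AEs/SAEs will be evaluated". A list of finer categories follows, introduced as optional: "The following ADA results may be evaluated as proportion of subjects in cohorts together with corresponding titer summaries". One of them is the treatment-emergent pattern, "Subjects who are ADA positive post-baseline and ADA negative at baseline". It is not linked to AEs or SAEs.

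SAP 2.1.2 and 4.2.9.7 put all ADA summaries on the safety set, which anyone with a single dose enters. SAP 3.5 schedules two ADA samples per subject, one before the first dose and one at Week 12.

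The exploratory outcome in Protocol 2.4 is the "incidence rate of positive anti-drug antibodies and characterization of their neutralizing potential". Protocol 8.4.4.7 plans a by-visit ADA summary by treatment group. It leaves the association with AEs/SAEs optional and gives no rule for baseline positives or missing samples. The rule in question is therefore the SAP's own, and SAP Section 6 lists no change on it.

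**The concern.** An ADA-by-AE comparison is normally read as asking whether subjects who developed antibodies on the drug had more events. The SAP's grouping answers a different question.

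- The positive group includes subjects whose reactivity preceded any drug, including placebo subjects.
- The negative group includes subjects with no information after exposure. There is no third class for them.

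The second fault may be related to the events themselves. Protocol 3.9.2 withdraws subjects for adverse events that rule out further dosing, and with one scheduled post-baseline sample a single missed visit removes all scheduled information. If untested leavers had events, counting them as negative raises the event rate in the negative group and can hide an association. Pre-dose positives whose reactivity has no bearing on events would dilute the positive group.

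**Working it through.** **Step 1: apply the rule to each pattern of results.**

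| Baseline | After first dose | Overall status under the SAP | Treatment-emergent? |
|---|---|---|---|
| positive | positive | positive | no (positive before dosing) |
| positive | negative | positive | no |
| positive | no sample | positive | no |
| negative | positive | positive | yes |
| negative | negative | negative | no |
| negative | no sample | negative | unknown |
| no sample | no sample | negative | unknown |

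Of the four patterns classed as positive, one is treatment-emergent. Of the three classed as negative, two contain no result after exposure.

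**Step 2: illustrate the size.** The documents state no ADA figure, so there is nothing to reproduce. Only the 40 subjects per arm come from the plan (SAP 1.3). Three quantities are assumed:

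- b, the share positive at baseline: 1% to 10%
- t, the share of baseline-negative, later-sampled subjects who turn positive: 1% to 10%
- m, the share with no post-baseline sample: 0 to 22.5%, taken as independent of b. The upper end borrows the plan's allowance for unevaluable biopsies, 1 − 31/40. It is not an ADA figure.

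Formulas for 40 treated subjects:

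- overall positive = 40 × [b + (1 − b)(1 − m)t]
- treatment-emergent = 40 × (1 − b)(1 − m)t
- negative with no post-baseline sample = 40 × (1 − b)m

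With b = 5%, t = 5%, m = 10%:

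- baseline positives: 40 × 0.05 = 2.0
- treatment-emergent: 40 × 0.95 × 0.90 × 0.05 = 1.71
- overall positive: 2.0 + 1.71 = 3.71
- untested negatives: 40 × 0.95 × 0.10 = 3.8

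| b | t | m | Overall positive | Treatment-emergent | Share positive before dosing | Untested negatives |
|---|---|---|---|---|---|---|
| 1% | 10% | 0 | 4.36 | 3.96 | 9% | 0 |
| 2% | 2% | 10% | 1.51 | 0.71 | 53% | 3.9 |
| 5% | 5% | 10% | 3.71 | 1.71 | 54% | 3.8 |
| 10% | 1% | 22.5% | 4.28 | 0.28 | 93% | 8.1 |

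Over the whole assumed grid, the share of positives that predate dosing runs from 9% to 93%. Where b equals t it is about 50% to 59%.

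**Step 3: the rate that would be read as incidence.** In the 5%/5%/10% case, overall status gives 3.71/40 = 9.3%. Counting treatment-emergent positives among the 40 × 0.90 = 36 subjects with a post-baseline result gives 1.71/36 = 4.75%.

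**The case against.** Several stronger conclusions are tempting, and the documents do not support them.

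- *That overall status fails to measure antibodies raised by tralokinumab.* It captures every treatment-emergent positive that is detected. The fault is that it does not separate them from pre-dose positives.
- *That everyone without a post-baseline sample becomes negative.* A baseline-positive subject without one is classed as positive. Only those with a negative or missing baseline fall into the negatives.
- *That incidence cannot be recovered from the planned outputs.* The by-visit summary in Protocol 8.4.4.7 is firm, is by treatment group and is not withdrawn in SAP Section 6. It shows Week 0 and Week 12 positivity separately, and SAP 4.1 has all data listed. This stands, but marginal counts by visit do not change the groups used for the AE/SAE association.
- *That early leavers go untested.* Protocol 3.9.2 asks for the end-of-treatment assessments at withdrawal where possible, and these include ADA. Protocol 5.5 adds neutralizing-antibody assessment at discontinuation as indicated. The untested share is therefore smaller than the withdrawal rate, but not zero, and the rule for those who remain is unchanged.
- *That event-triggered samples should be excluded because they give reactors an extra chance to test positive.* Under Protocol 6.7 a sample "should be drawn during the event for anti-drug antibody/neutralizing anti-body" testing, so sampling is indeed unequal. Dropping these samples could nevertheless discard a safety-relevant positive in a subject who then leaves without another sample.

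It can also be said that grouping any-time positives is a defensible choice, since pre-existing antibodies might matter on exposure, and that with a few positives the comparison is descriptive under any definition. Both points limit the importance. Neither justifies counting untested subjects as negative or leaving the treatment-emergent comparison unplanned.

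**Conclusion.** The rule, as written, misclassifies subjects for the one ADA comparison with AEs/SAEs that the SAP commits to. That follows from the text and needs no assumption about rates.

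The size cannot be determined from the documents. If baseline positivity is nil, the effect is small: with t = 2% and m = 20%, the reported rate is 0.02 × 0.80 = 1.6% instead of 2%, a difference of 40 × 0.004 = 0.16 of a subject. If baseline and emergent rates are similar, half or more of the overall positives would predate dosing.

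This is an exploratory immunogenicity and safety summary. It should be corrected because the repair is easy, and it has no bearing on the primary or secondary analyses or on the sample size.

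**What to change.** In SAP 4.2.9.7:

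- Make the listed category "Subjects who are ADA positive post-baseline and ADA negative at baseline" a firm analysis. Use it, by treatment group, for ADA incidence and for the association with AEs/SAEs.
- Take as denominator the subjects with at least one post-baseline ADA result, and show those with none as not evaluable, not as negative.
- Show baseline-positive subjects in a separate row with their titres, so that any rise after dosing can be seen.
- Keep event-triggered samples in the status, but flag subjects whose only positive result comes from such a sample.

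The cost is SAP wording and table programming, with no new samples. The downside is a slightly smaller denominator and one or two more table rows.
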